Appendix A

Trial ID	pNDA27
Trial Name (with web links)	ROCKET AF
Trial Name (with pdf links)	ROCKET AF
NCT	NCT00403767
Trial category	Primary indication
Therapeutic Area	Cardiology/Vascular Diseases
Study batch	NOACs
RCT Category	4a- Unintended S with label change
Brand Name	Xarelto
Generic Name	rivaroxaban
Sponsor	Janssen Pharmaceuticals
Year	2011
Measurable endpoint	Primary endpoint of stroke and systemic embolism
Exposure	Rivaroxaban
Comparator	Warfarin
Population	patients with nonvalvular atrial fibrillation who were at increased risk for stroke
Trial finding	HR = 0.79 (95% CI 0.66–0.96)
No. of Patients	14,264
Non-inferiority margin	HR = 1.46
Power	0.95 power of 95% to calculate a noninferiority margin of 1.46 with a one-sided alpha level of 0.025.
Blinding	Double-blinded
Statistical Method	Alternative hypothesis of non-inferiority (NI) by a NI margin of 1.46 in hazard ratio (HR) based on on-treatment data from the per protocol population. The required number of primary efficacy endpoint events was determined based on the following assumptions: NI margin of 1.46, 1-sided alpha of 0.025, power of >95% when true HR is 1, and exponential distributions. The margin was selected based on clinical appropriateness and quantitative analysis of relevant studies in Hart et al.
Approval indication	For the reduction in the risk of stroke and systemic embolism resulting from atrial fibrillation

Appendix A

Dialysis codes
ESRD, defined as 2 codes (either inpatient or outpatient), separated by at least 30 days
Codes include:
- ICD9 prox codes:
39.95, Hemodialysis
54.98, Peritoneal dialysis
- ICD9 dx codes:
585.5x, Chronic kidney disease, Stage V (for ESRD with no mention of dialysis)
585.6x, End stage renal disease (for ESRD with dialysis)
V56.0x, encounter for dialysis NOS
V56.8x, encounter for peritoneal dialysis
V45.1x, renal dialysis status
- CPT4 codes:
90957, 90960, ESRD related services monthly, for patients 12-19 and 20 years of age and older; with 4 or more face-to-face physician visits per month
90958, 90961, ESRD related services monthly, for patients 12-19 and 20 years of age and older; with 2-3 face-to-face physician visits per month
90959, 90962, ESRD related services monthly, for patients 12-19 and 20 years of age and older; with 1 face-to-face physician visit per month
90920, 90921, ESRD related services per full month; for patients 12-19 and twenty years of age and over
90924, 90925, ESRD related services (less than full month), per day; for patients 12-19 and twenty years of age and over
90935, Hemodialysis procedure with single physician evaluation
90937, Hemodialysis procedure requiring repeated evaluation(s) with or without substantial revision of dialysis prescription
90945, Dialysis procedure other than hemodialysis (eg, peritoneal dialysis, hemofiltration, or other continuous renal replacement therapies), with single physician evaluation
90947, Dialysis procedure other than hemodialysis (eg, peritoneal dialysis, hemofiltration, or other continuous renal replacement therapies) requiring repeated physician evaluations, with or without substantial revision of dialysis prescription
90965, 90966, ESRD related services for home dialysis per full month, for patients 12-19 and 20 years of age and older
90969, 90970, ESRD related services for dialysis less than a full month of service, per day; for patients 12-19 and 20 years of age and older
90989, Dialysis training, patient, including helper where applicable, any mode, completed course
90993, Dialysis training, patient, including helper where applicable, any mode, course not completed, per training session
90999, Unlisted dialysis procedure, inpatient or outpatient
99512, Home visit for hemodialysis
- HCPCS codes:
G0257, Unscheduled or emergency dialysis treatment for ESRD patient in a hospital outpatient dept. that is not certified as an ESRD facility
G0314, G0317, ESRD related services during the course of treatment, for patients 12-19 and 20 yrs of age an over to include monitoring for the adequacy of nutrition, etc. w/4 or more physician visit per month
G0315, G0318, ESRD related services during the course of treatment, for patients 12-19 and 20yrs of age and over to include monitoring for the adequacy of nutrition etc w/2 or 3 physician visit per month

Appendix A

~~adequacy of nutrition, etc. w/ 2 or 3 physician visit per month~~

G0316, G0319, ESRD related services during the course of treatment, for patients 12-19 and 20 yrs of age and over to include monitoring for the adequacy of nutrition, etc. w/1 physician visit per month

G0322, G0323, ESRD related services for home dialysis patients per full month: for patients 12-19 and 20 yrs of age and over to include monitoring for adequacy of nutrition and etc.

G0326, G0327, ESRD related services for home dialysis (less than full month), per day; for patients 12-19 and 20 yrs of age and over

S9335, Home therapy, hemodialysis; administrative services, professional pharmacy services, care coordination, and all necessary supplies and equipment (drugs and nursing services coded separately), per diem

S9339, Home therapy, peritoneal dialysis, administrative services, care coordination and all necessary supplies and equipment, per diem

OR

Kidney transplant, defined as either 1 inpatient or 1 outpatient code

Codes include:

-ICD9 dx codes:

V42.0x, Kidney transplant status

996.81 Complications of transplanted kidney

-ICD9 prox codes:

55.6x, Transplant of kidney (Exclude 55.61)

- CPT4 codes:

50360, Renal allotransplantation, implantation, graft, w/o donor & recipient nephrectomy

Appendix A

Bleeding Codes
423.0 - (ICD9) HEMOPERICARDIUM
430 - (ICD9) SUBARACHNOID HEMORRHAGE
431 - (ICD9) INTRACEREBRAL HEMORRHAGE
432.0 - (ICD9) NONTRAUMATIC EXTRADURAL HEMORRHAGE
432.1 - (ICD9) SUBDURAL HEMORRHAGE
432.9 - (ICD9) UNSPECIFIED INTRACRANIAL HEMORRHAGE
459.0 - (ICD9) HEMORRHAGE UNSPECIFIED
531.0 - (ICD9) ACUTE GASTRIC ULCER WITH HEMORRHAGE
531.00 - (ICD9) ACUTE GASTRIC ULCER WITH HEMORRHAGE WITHOUT OBSTRUCTION
531.01 - (ICD9) ACUTE GASTRIC ULCER WITH HEMORRHAGE WITH OBSTRUCTION
531.2 - (ICD9) ACUTE GASTRIC ULCER WITH HEMORRHAGE AND PERFORATION
531.20 - (ICD9) ACUTE GASTRIC ULCER WITH HEMORRHAGE AND PERFORATION WITHOUT OBSTRUCTION
531.21 - (ICD9) ACUTE GASTRIC ULCER WITH HEMORRHAGE AND PERFORATION WITH OBSTRUCTION
531.4 - (ICD9) CHRONIC OR UNSPECIFIED GASTRIC ULCER WITH HEMORRHAGE
531.40 - (ICD9) CHRONIC OR UNSPECIFIED GASTRIC ULCER WITH HEMORRHAGE WITHOUT OBSTRUCTION
531.41 - (ICD9) CHRONIC OR UNSPECIFIED GASTRIC ULCER WITH HEMORRHAGE WITH OBSTRUCTION
531.6 - (ICD9) CHRONIC OR UNSPECIFIED GASTRIC ULCER WITH HEMORRHAGE AND PERFORATION
531.60 - (ICD9) CHRONIC OR UNSPECIFIED GASTRIC ULCER WITH HEMORRHAGE AND PERFORATION WITHOUT OBSTRUCTION
531.61 - (ICD9) CHRONIC OR UNSPECIFIED GASTRIC ULCER WITH HEMORRHAGE AND PERFORATION WITH OBSTRUCTION
532.0 - (ICD9) ACUTE DUODENAL ULCER WITH HEMORRHAGE
532.00 - (ICD9) ACUTE DUODENAL ULCER WITH HEMORRHAGE WITHOUT OBSTRUCTION
532.01 - (ICD9) ACUTE DUODENAL ULCER WITH HEMORRHAGE WITH OBSTRUCTION
532.2 - (ICD9) ACUTE DUODENAL ULCER WITH HEMORRHAGE AND PERFORATION
532.20 - (ICD9) ACUTE DUODENAL ULCER WITH HEMORRHAGE AND PERFORATION WITHOUT OBSTRUCTION
532.21 - (ICD9) ACUTE DUODENAL ULCER WITH HEMORRHAGE AND PERFORATION WITH OBSTRUCTION
532.4 - (ICD9) CHRONIC OR UNSPECIFIED DUODENAL ULCER WITH HEMORRHAGE
532.40 - (ICD9) CHRONIC OR UNSPECIFIED DUODENAL ULCER WITH HEMORRHAGE WITHOUT OBSTRUCTION
532.41 - (ICD9) CHRONIC OR UNSPECIFIED DUODENAL ULCER WITH HEMORRHAGE WITH OBSTRUCTION
532.6 - (ICD9) CHRONIC OR UNSPECIFIED DUODENAL ULCER WITH HEMORRHAGE AND PERFORATION
532.60 - (ICD9) CHRONIC OR UNSPECIFIED DUODENAL ULCER WITH HEMORRHAGE AND PERFORATION WITHOUT OBSTRUCTION
532.61 - (ICD9) CHRONIC OR UNSPECIFIED DUODENAL ULCER WITH HEMORRHAGE AND PERFORATION WITH OBSTRUCTION
533.0 - (ICD9) ACUTE PEPTIC ULCER OF UNSPECIFIED SITE WITH HEMORRHAGE
533.00 - (ICD9) ACUTE PEPTIC ULCER OF UNSPECIFIED SITE WITH HEMORRHAGE WITHOUT OBSTRUCTION
533.01 - (ICD9) ACUTE PEPTIC ULCER OF UNSPECIFIED SITE WITH HEMORRHAGE WITH OBSTRUCTION
533.2 - (ICD9) ACUTE PEPTIC ULCER OF UNSPECIFIED SITE WITH HEMORRHAGE AND PERFORATION
533.20 - (ICD9) ACUTE PEPTIC ULCER OF UNSPECIFIED SITE WITH HEMORRHAGE AND PERFORATION WITHOUT OBSTRUCTION
533.21 - (ICD9) ACUTE PEPTIC ULCER OF UNSPECIFIED SITE WITH HEMORRHAGE AND PERFORATION WITH OBSTRUCTION
533.4 - (ICD9) CHRONIC OR UNSPECIFIED PEPTIC ULCER OF UNSPECIFIED SITE WITH HEMORRHAGE
533.40 - (ICD9) CHRONIC OR UNSPECIFIED PEPTIC ULCER OF UNSPECIFIED SITE WITH HEMORRHAGE WITHOUT OBSTRUCTION

Appendix A

533.41 - (ICD9) CHRONIC OR UNSPECIFIED PEPTIC ULCER OF UNSPECIFIED SITE WITH HEMORRHAGE WITH OBSTRUCTION
533.6 - (ICD9) CHRONIC OR UNSPECIFIED PEPTIC ULCER OF UNSPECIFIED SITE WITH HEMORRHAGE AND PERFORATION
533.60 - (ICD9) CHRONIC OR UNSPECIFIED PEPTIC ULCER OF UNSPECIFIED SITE WITH HEMORRHAGE AND PERFORATION WITHOUT OBSTRUCTION
533.61 - (ICD9) CHRONIC OR UNSPECIFIED PEPTIC ULCER OF UNSPECIFIED SITE WITH HEMORRHAGE AND PERFORATION WITH OBSTRUCTION
534.0 - (ICD9) ACUTE GASTROJEJUNAL ULCER WITH HEMORRHAGE
534.00 - (ICD9) ACUTE GASTROJEJUNAL ULCER WITH HEMORRHAGE WITHOUT OBSTRUCTION
534.01 - (ICD9) ACUTE GASTROJEJUNAL ULCER WITH HEMORRHAGE WITH OBSTRUCTION
534.2 - (ICD9) ACUTE GASTROJEJUNAL ULCER WITH HEMORRHAGE AND PERFORATION
534.20 - (ICD9) ACUTE GASTROJEJUNAL ULCER WITH HEMORRHAGE AND PERFORATION WITHOUT OBSTRUCTION
534.21 - (ICD9) ACUTE GASTROJEJUNAL ULCER WITH HEMORRHAGE AND PERFORATION WITH OBSTRUCTION
534.4 - (ICD9) CHRONIC OR UNSPECIFIED GASTROJEJUNAL ULCER WITH HEMORRHAGE
534.40 - (ICD9) CHRONIC OR UNSPECIFIED GASTROJEJUNAL ULCER WITH HEMORRHAGE WITHOUT OBSTRUCTION
534.41 - (ICD9) CHRONIC OR UNSPECIFIED GASTROJEJUNAL ULCER WITH HEMORRHAGE WITH OBSTRUCTION
534.6 - (ICD9) CHRONIC OR UNSPECIFIED GASTROJEJUNAL ULCER WITH HEMORRHAGE AND PERFORATION
534.60 - (ICD9) CHRONIC OR UNSPECIFIED GASTROJEJUNAL ULCER WITH HEMORRHAGE AND PERFORATION WITHOUT OBSTRUCTION
534.61 - (ICD9) CHRONIC OR UNSPECIFIED GASTROJEJUNAL ULCER WITH HEMORRHAGE AND PERFORATION WITH OBSTRUCTION
562.02 - (ICD9) DIVERTICULOSIS OF SMALL INTESTINE WITH HEMORRHAGE
562.03 - (ICD9) DIVERTICULITIS OF SMALL INTESTINE WITH HEMORRHAGE
562.12 - (ICD9) DIVERTICULOSIS OF COLON WITH HEMORRHAGE
562.13 - (ICD9) DIVERTICULITIS OF COLON WITH HEMORRHAGE
568.81 - (ICD9) HEMOPERITONEUM (NONTRAUMATIC)
569.3 - (ICD9) HEMORRHAGE OF RECTUM AND ANUS
569.83 - (ICD9) PERFORATION OF INTESTINE
569.85 - (ICD9) ANGIODYSPLASIA OF INTESTINE WITH HEMORRHAGE
569.86 - (ICD9) DIEULAFOY LESION (HEMORRHAGIC) OF INTESTINE
578.0 - (ICD9) HEMATEMESIS
578.1 - (ICD9) BLOOD IN STOOL
578.9 - (ICD9) HEMORRHAGE OF GASTROINTESTINAL TRACT UNSPECIFIED
719.1 - (ICD9) HEMARTHROSIS
719.10 - (ICD9) HEMARTHROSIS SITE UNSPECIFIED
719.11 - (ICD9) HERARTHROSIS INVOLVING SHOULDER REGION
719.12 - (ICD9) HEMARTHROSIS INVOLVING UPPER ARM
719.13 - (ICD9) HEMARTHROSIS INVOLVING FOREARM
719.14 - (ICD9) HEMARTHROSIS INVOLVING HAND
719.15 - (ICD9) HEMARTHROSIS INVOLVING PELVIC REGION AND THIGH
719.16 - (ICD9) HEMARTHROSIS INVOLVING LOWER LEG
719.17 - (ICD9) HEMARTHROSIS INVOLVING ANKLE AND FOOT
719.18 - (ICD9) HEMARTHROSIS INVOLVING OTHER SPECIFIED SITES

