Appendix A

1f	Active endocarditis	
Measured 180 days prior to and including day of drug initiation in any diagnosis position and inpatient or outpatient care setting:
 
Endocarditis: ICD-9 diagnosis: 421.xx , 424.9x ICD-10 diagnosis: I33.xx, I38.xx, I39.xx
	
Tan, Charlie et al. "Accuracy of administrative data for identification of patients with infective endocarditis." International journal of cardiology vol. 224 (2016): 162-164. doi:10.1016/j.ijcard.2016.09.030

2	Hemorrhage Risk-Related Criteria		
2a	Active internal bleeding	
Measured 180 days prior to and including day of drug initiation in any diagnosis position and inpatient or outpatient care setting: Refer to the 'Bleeding' sheet for detailed codes (includes GI bleeding, intracranial, intra-articular bleeding mentioned in exclusion 2b)
	
2b	
History of or condition associated with increased bleeding risk including, but not limited to:
 
 - Major surgical procedure or trauma within 30 days before the randomization visit - Clinically significant gastrointestinal bleeding within 6 months before the randomization visit - History of intracranial, intraocular, spinal, or atraumatic intra-articular bleeding - Chronic hemorrhagic disorder - Known intracranial neoplasm, arteriovenous malformation, or aneurysm 	
Measured 30 days prior to and including day of drug initiation in diagnosis position and inpatient or outpatient care setting:
 
1) Major surgery: Major surgery selected from procedure codes range 40.x- 84.x -OR-
 
2) Hemorrhagic disorder (Bleeding diathesis) 286.x Coagulation defects 287.x Purpura and other hemorrhagic conditions -OR-
 
3) Intracranial neoplasm, AV malformation, aneurysm Intracranial neoplasm ICD-9 diagnosis: 225.xx ICD-10 diagnosis: D33.xx AV malformation ICD-9 diagnosis: 747.81 ICD-10 diagnosis: Q28.2x Cerebral aneurysm: ICD-9 diagnosis: 437.3x ICD-10 diagnosis: I67.1
	
2c	Planned invasive procedure with potential for uncontrolled bleeding, including major surgery	N/A	
2d	Platelet count <90,000/ μ L at the screening visit	
Measured 30 days prior to and including day of drug initiation in any diagnosis position and inpatient or outpatient care setting:
 
Thrombocytopenia: ICD-9 diagnosis: 287.3x, 287.4x, 287.5x
	

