Appendix A

K25.6 - (ICD10) Chronic or unspecified gastric ulcer with both hemorrhage and perforation
K26.0 - (ICD10) Acute duodenal ulcer with hemorrhage
K26.2 - (ICD10) Acute duodenal ulcer with both hemorrhage and perforation
K26.4 - (ICD10) Chronic or unspecified duodenal ulcer with hemorrhage
K26.6 - (ICD10) Chronic or unspecified duodenal ulcer with both hemorrhage and perforation
K27.0 - (ICD10) Acute peptic ulcer, site unspecified, with hemorrhage
K27.2 - (ICD10) Acute peptic ulcer, site unspecified, with both hemorrhage and perforation
K27.4 - (ICD10) Chronic or unspecified peptic ulcer, site unspecified, with hemorrhage
K27.6 - (ICD10) Chronic or unspecified peptic ulcer, site unspecified, with both hemorrhage and perforation
K28.0 - (ICD10) Acute gastrojejunal ulcer with hemorrhage
K28.2 - (ICD10) Acute gastrojejunal ulcer with both hemorrhage and perforation
K28.4 - (ICD10) Chronic or unspecified gastrojejunal ulcer with hemorrhage
K28.6 - (ICD10) Chronic or unspecified gastrojejunal ulcer with both hemorrhage and perforation
K55.21 - (ICD10) Angiodysplasia of colon with hemorrhage
K56.60 - (ICD10) Unspecified intestinal obstruction
K57.01 - (ICD10) Diverticulitis of small intestine with perforation and abscess with bleeding
K57.11 - (ICD10) Diverticulosis of small intestine without perforation or abscess with bleeding
K57.13 - (ICD10) Diverticulitis of small intestine without perforation or abscess with bleeding
K57.21 - (ICD10) Diverticulitis of large intestine with perforation and abscess with bleeding
K57.31 - (ICD10) Diverticulosis of large intestine without perforation or abscess with bleeding
K57.33 - (ICD10) Diverticulitis of large intestine without perforation or abscess with bleeding
K57.41 - (ICD10) Diverticulitis of both small and large intestine with perforation and abscess with bleeding
K57.51 - (ICD10) Diverticulosis of both small and large intestine without perforation or abscess with bleeding
K57.53 - (ICD10) Diverticulitis of both small and large intestine without perforation or abscess with bleeding
K57.81 - (ICD10) Diverticulitis of intestine, part unspecified, with perforation and abscess with bleeding
K57.91 - (ICD10) Diverticulosis of intestine, part unspecified, without perforation or abscess with bleeding
K57.93 - (ICD10) Diverticulitis of intestine, part unspecified, without perforation or abscess with bleeding
K62.5 - (ICD10) Hemorrhage of anus and rectum
K63.1 - (ICD10) Perforation of intestine (nontraumatic)

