Appendix A

K63.81 - (ICD10) Dieulatoy lesion of intestine
K66.1 - (ICD10) Hemoperitoneum
K92.0 - (ICD10) Hematemesis
K92.1 - (ICD10) Melena
K92.2 - (ICD10) Gastrointestinal hemorrhage, unspecified
M25.00 - (ICD10) Hemarthrosis, unspecified joint
M25.011 - (ICD10) Hemarthrosis, right shoulder
M25.012 - (ICD10) Hemarthrosis, left shoulder
M25.019 - (ICD10) Hemarthrosis, unspecified shoulder
M25.021 - (ICD10) Hemarthrosis, right elbow
M25.022 - (ICD10) Hemarthrosis, left elbow
M25.029 - (ICD10) Hemarthrosis, unspecified elbow
M25.031 - (ICD10) Hemarthrosis, right wrist
M25.032 - (ICD10) Hemarthrosis, left wrist
M25.039 - (ICD10) Hemarthrosis, unspecified wrist
M25.041 - (ICD10) Hemarthrosis, right hand
M25.042 - (ICD10) Hemarthrosis, left hand
M25.049 - (ICD10) Hemarthrosis, unspecified hand
M25.051 - (ICD10) Hemarthrosis, right hip
M25.052 - (ICD10) Hemarthrosis, left hip
M25.059 - (ICD10) Hemarthrosis. unspecified hip

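### The Bleeding sheet names no gastritis, Mallory-Weiss, esophageal or gastric/duodenal angiodysplasia bleed, so exclusion 2a can miss patients coded only with one of these diagnoses

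*Combined protocol and SAP*

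**What the plan says.** In the Appendix A exclusion table, the trial's criterion 2b includes "Clinically significant gastrointestinal bleeding within 6 months before the randomization visit", with no limit by site within the gut. The claims version is placed under row 2a. It looks back 180 days, in any diagnosis position and in inpatient or outpatient care, and refers to the Bleeding sheet, which it says "includes GI bleeding, intracranial, intra-articular bleeding mentioned in exclusion 2b".

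The sheet (Appendix A, Bleeding Codes) prints both ICD-9 and ICD-10 entries. Its gastrointestinal content is:

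- bleeding gastric, duodenal, peptic and gastrojejunal ulcers (531–534, K25–K28);
- diverticular bleeds (562.x, K57.x);
- intestinal vascular lesions, such as "569.85 - (ICD9) ANGIODYSPLASIA OF INTESTINE WITH HEMORRHAGE" and "K55.21 - (ICD10) Angiodysplasia of colon with hemorrhage", with Dieulafoy lesions of the intestine (569.86, K63.81);
- rectal and anal bleeding (569.3, K62.5), hemoperitoneum and intestinal perforation;
- non-specific codes 578.0, 578.1, 578.9, K92.0, K92.1 and "K92.2 - (ICD10) Gastrointestinal hemorrhage, unspecified";
- two bleeding-control procedures, 44.43 and 0W3P8ZZ.

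The general hemorrhage codes 459.0 and R58 are also listed.

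**The concern.** Row 2a says that this single list carries the gastrointestinal part of criterion 2b, yet several upper-GI sources of bleeding are absent by name. The pattern looks like an oversight. Angiodysplasia and Dieulafoy lesions appear for the intestine but not for the stomach or duodenum. The list also includes a procedure for endoscopic control of gastric or duodenal bleeding, so upper-GI bleeding was evidently meant to be covered. No reason for the omission is given.

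A patient whose recent bleed was recorded only under one of the absent diagnoses passes 2a, although the trial would have barred that patient. Section 5.2.2 undertakes to follow the trial's criteria as closely as possible, so what is at stake is how faithfully eligibility is emulated.

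**Working it through.** **1. Is the omission real, or lost text?** The printed list runs in code order, so a gap shows as a jump between neighbouring lines.

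| Line before the gap | Next line | Blocks skipped |
|---|---|---|
| "459.0 - (ICD9) HEMORRHAGE UNSPECIFIED" | 531.0 | 530.x |
| 534.61 | "562.02 - (ICD9) DIVERTICULOSIS OF SMALL INTESTINE WITH HEMORRHAGE" | 535.x, 537.x |
| I62.9 | K25.0 | K20–K22 |
| "K28.6 - (ICD10) Chronic or unspecified gastrojejunal ulcer with both hemorrhage and perforation" | "K55.21 - (ICD10) Angiodysplasia of colon with hemorrhage" | K29.x, K31.x |

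Each pair is adjacent on the same page, so none of the jumps is a page-break loss. A search by code prefix finds no entries for 530, 535, 537, K22, K29 or K31. No label on the sheet mentions gastritis, duodenitis, Mallory-Weiss or the esophagus, and none gives angiodysplasia or a Dieulafoy lesion of the stomach or duodenum.

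**2. Who can slip through?** Row 2a is met by any listed code in 180 days, in any position and setting. A patient with a missing diagnosis is still removed if any claim in the window carries 578.0, 578.1, 578.9, K92.0–K92.2, 459.0, R58, 44.43 or 0W3P8ZZ. Only patients with none of these, and no other listed code, are retained.

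**3. The plan's own count at 2a (Section 5.3).**

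- Optum: 54,694 − 3,413 = 51,281
- Truven: 61,418 − 2,716 = 58,702
- Medicare: 177,460 − 8,256 = 169,204

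All three agree with the flowchart. Total removed: 3,413 + 2,716 + 8,256 = 14,385.

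**4. Illustrative size.** The documents give no count for the missing codes. Assume that they would add 4–8% to those removed at 2a:

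- 0.04 × 14,385 = 575; 0.08 × 14,385 = 1,151.
- Remaining after 2a: 51,281 + 58,702 + 169,204 = 279,187. Final cohort: 40,604 + 50,085 + 133,230 = 223,919. Share surviving the later exclusions: 223,919 / 279,187 = 0.802.
- 575 × 0.802 ≈ 461; 1,151 × 0.802 ≈ 923.
- 461 / 223,919 = 0.21%; 923 / 223,919 = 0.41%.

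**5. Effect on power.** Section 10 gives 1,034.57 expected events and pooled superiority power of 0.9665 at HR 0.79. The Schoenfeld form, power = Φ(|ln HR| × √(events/4) − 1.96), gives 0.2357 × 16.08 − 1.96 = 1.83, hence 0.9665, which reproduces the plan. With 0.5% fewer events, power is 0.9657; with 2% fewer, 0.9635.

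**6. Residual GI-bleed covariates (Appendix B, unmatched).** After the exclusions, Medicare still shows 86 + 31 = 117 upper GI bleeds and 1,049 + 509 = 1,558 lower or unspecified GI bleeds among 92,403 + 40,652 = 133,055 patients (0.09% and 1.17%). Optum and MarketScan show 0 for both. The covariate code lists are not given, so these counts cannot be attributed to the gap.

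**The case against.** The strongest reply is that the list is broader than its named lesions suggest. Hematemesis, melena or blood in stool, unspecified GI hemorrhage and endoscopic control of bleeding are ways in which an upper-GI bleed reaches a claim, and 180 days in any position and setting is a wide net. This stands. It narrows the gap but does not close it, because nothing in the documents says that every such patient also has a non-specific code.

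Four further points:

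- *Over-exclusion.* The trial barred only clinically significant bleeds, whereas the sheet accepts any outpatient rectal-bleeding code and even unspecified intestinal obstruction (K56.60). This is fair, but looseness elsewhere is no reason to omit upper-GI diagnoses.
- *Later exclusions.* Row 3h removes several anemia codes, including one labelled as following acute hemorrhage, so attrition after a bleed is probably above average. This stands and pulls the illustration down.
- *Confounding.* A reader might infer that the treatment comparison is biased. The documents do not show this. Pooled peptic ulcer disease is 15.2% for warfarin and 19.9% for rivaroxaban before matching, but 19.3% and 19.1% after it; matched differences in HAS-BLED and proton pump inhibitor use are 0.00. No differential retention by arm is shown. This does not prove adjustment for the missed bleeds themselves, since the GI-bleed covariates are 0 in Optum and MarketScan.
- *ICD-10 lists held elsewhere.* Appendix A says that full ICD-10 lists are stored outside the document. This sheet prints its ICD-10 codes, however, and the ICD-9 gap stands regardless.

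**Conclusion.** The point holds as a small gap in eligibility coding. Exclusion 2a does not name several upper-GI bleeding diagnoses that fall within the trial criterion it is said to implement, and patients coded only with one of them can enter.

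The size is unknown. The 460–920 patients (0.2–0.4% of the final cohort) rest on a 4–8% increment that has no source in the documents, and on average attrition after 2a. The base of 14,385 also contains intracranial, joint and pericardial bleeds, so it is a loose denominator for a GI increment. The effect on power is negligible, and the effect on the stroke or systemic embolism estimate is likely very small.

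Two stronger readings are not supported. A reader might infer that recent upper-GI bleeds generally go unexcluded; the ulcer, non-specific and procedure codes contradict that. A reader might also infer that the major-bleeding control outcome misses these events and so cannot be compared with the trial's 1.04. Only row 2a refers to the sheet, and nothing states that the control outcome uses it.

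**What to change.** Add the upper-GI hemorrhage diagnoses to the Bleeding sheet: ICD-9 530.21, 530.7, 530.82, 535.x1, 537.83 and 537.84; ICD-10 K22.11, K22.6, K29.x1, K31.811 and K31.82. These code numbers are not in the protocol and should be checked against the code books before use. Then re-run exclusion 2a, the propensity-score match and the balance tables, and report how many patients change, by arm and database. If the team prefers to leave the list as it is, it should state why the non-specific codes suffice and give the count that supports this.

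The cost is a code-list edit, a re-run and a refresh of the balance and final power review, which Section 10 dates to September 2020. The likely loss is under 1% of patients: even with no later attrition, the upper illustration is 1,151 / 223,919 = 0.51%. The comparative-analysis date in Section 13 is blank, so on the document as it stands the change can be made before outcome results are seen.
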